11.3.1 Summary Tables for Adverse Events

All pre-dose AEs (as defined in [Section 11.3](#)) will be excluded from the summary tables, but will be listed.

Descriptive statistical methods will be used to summarise the TEAE data.

The number and percentage of subjects reporting each TEAE will be presented for both SOC and PT. For summaries by SOC and PT, with the exception of TEAEs by severity and relationship to IMP, the number of subjects, and the number of events will be summarised. For summaries by severity and relationship, only the number of subjects will be summarised.

For counts of subjects experiencing events the following will apply:

- A subject experiencing TEAEs in more than one body system, within a study period, will be counted once in the total number of subjects with TEAEs in that study period
- A subject with more than 1 TEAE in the same SOC, within a study period, counts only once at the SOC level
- A subject with more than 1 TEAE in the same PT, within a study period, counts only once at the PT level

For TEAE event counts, all events are included.

When it is necessary to calculate percentages, the denominator will be the total number of subjects in the safety analysis set for that regimen or study period and the numerator will be the total number of subjects reporting a TEAE within the relevant category.

Summaries presented for SOC and PT will be presented in descending order of frequency overall i.e. most frequently reported SOC in the study and then by most frequently reported PT in the study within each SOC.

11.3.1.1 Overall Summary of Adverse Events

The following will be summarised by regimen and overall for the safety analysis set:

- Number and percentage of subjects reporting TEAEs
- Number and percentage of subjects reporting severe TEAEs
- Number and percentage of subjects reporting ADRs
- Number and percentage of subjects reporting serious TEAEs
- Number and percentage of subjects reporting TEAEs leading to subject withdrawal
- Number and percentage of subjects reporting TEAEs leading to death
- Total number of TEAEs
- Total number of severe TEAEs
- Total number of IMP-related ADRs

- Total number of serious TEAEs
- Total number of TEAEs leading to subject withdrawal
- Total number of TEAEs leading to death

11.3.1.2 Summary of Treatment-Emergent Adverse Events

All subjects reporting TEAEs will be summarised by regimen and overall. Counts will be given for number of subjects and number of events. Subjects experiencing more than 1 TEAE within a regimen/overall will be counted only once for number of subjects but will be counted more than once for number of events.

Additionally, subjects reporting TEAEs will be summarised for SOC and PT by regimen and overall. Counts will be given for number of subjects and number of events.

11.3.1.3 Summary of Treatment-Emergent Adverse Events by Severity

All subjects reporting TEAEs will be summarised by severity (i.e. mild, moderate, or severe) and regimen. Counts will be given for number of subjects, not number of events. Counts will be given by maximum severity (i.e., subjects experiencing more than 1 TEAE within a regimen will be counted only once using the most severe episode).

Additionally, subjects reporting TEAEs will be summarised for SOC and PT by maximum severity (i.e., mild, moderate, or severe) and regimen. Counts will be given for total number of subjects, not for events. Counts by maximum severity will be given (i.e., subjects experiencing more than 1 TEAE within a regimen will be counted only once within each SOC and PT using the most severe episode).

11.3.1.4 Summary of Treatment-Emergent Adverse Events by Relationship to IMP

All subjects reporting TEAEs will be summarised by relationship to IMP (i.e., unrelated, possibly related, or related) and regimen. Counts will be given for number of subjects, not number of events. Counts will be given by the closest relationship to IMP (i.e., subjects experiencing more than 1 TEAE within a regimen will be counted only once using the most closely related event).

Additionally, subjects reporting TEAEs will be summarised for SOC and PT by closest relationship to IMP (i.e. unrelated, possibly related, or related) and regimen. Counts will be given for total number of subjects, not for events. Counts by closest relationship will be given (i.e., subjects experiencing more than 1 TEAE within a regimen will be counted only once within each SOC and PT using the most closely related event).

11.3.1.5 Summary of Adverse Drug Reactions (ADRs)

All subjects reporting ADRs will be summarised by regimen. Counts will be given for number of subjects and number of events. Subjects experiencing more than 1 ADR within a regimen will be counted only once for number of subjects but will be counted more than once for number of events.

Additionally, subjects reporting ADRs will be summarised for SOC and PT by regimen. Counts will be given for number of subjects and number of events.

11.3.1.6 Summary of Serious Adverse Events

All subjects reporting treatment-emergent serious adverse events (SAEs) will be summarised by regimen. Counts will be given for number of subjects and number of events. Subjects experiencing more than 1 SAE within a regimen will be counted only once for number of subjects but will be counted more than once for number of events.

Additionally, subjects reporting treatment-emergent SAEs will be summarised for SOC and PT by regimen. Counts will be given for number of subjects and number of events.

11.3.2 Listings for Adverse Events

All pre-dose AEs (as defined in [Section 11.3](#)) will be listed including SOC and PT.

A separate data listing of all TEAEs will be provided including the SOC and PT. In addition, a listing of all SAEs will be provided.

11.4 Laboratory Evaluations

The details of sample collection for laboratory safety analysis are described in the study protocol.

Where a value is provided by the safety laboratory as either above or below the limit of detection (LOD), this will be set to the respective LOD itself for descriptive summaries. No imputations will be made in the individual listings.

11.4.1 Summary Tables for Laboratory Evaluations

Haematology and clinical chemistry data will be summarised (n, mean, SD, median, minimum, and maximum) for each laboratory parameter at each time point, including changes from baseline (Day -1, Admission for Period 1 and Day 1, Pre-dose for Periods 2 to 4) at each scheduled post-baseline time point by regimen.

Shift tables from baseline to each scheduled post-baseline time point (with respect to the number and percentage of subjects with values below, within or above the reference range) will be presented by regimen. Percentages will be based on the number of subjects with measurements at baseline and the relevant post-baseline time point.

For fasting-sensitive laboratory parameters (i.e., glucose), results taken in the non-fasted state (i.e., LBFAST=N) will not be included in summary statistics by time point or be used in derivations of changes from baseline. For tabulations (e.g., shift tables), both fasted and non-fasted results will be pooled and used in the tabulations, using the appropriate fasted or non-fasted reference range. All results (fasted or non-fasted) will be listed with non-fasted data flagged.

Reference ranges for each laboratory parameter will be presented for the relevant parameter in each summary table.

11.4.2 Listings for Laboratory Evaluations

The sample collection data (e.g., collection times) for laboratory analysis and urinalysis data will be listed.

All individual subject data for planned haematology, clinical chemistry, and urinalysis data, including derivations, such as change from baseline, will be listed. If applicable, data from unscheduled laboratory tests will also be listed and flagged with a “#” to indicate that it will not be used in the summary statistics. In these listings, individual data will be flagged with an “H” or an “L” for values that are higher or lower than their reference ranges, respectively.

Separate listings of all haematology, clinical chemistry, and urinalysis values outside their reference ranges by subject will also be provided. Reference ranges will be supplied by the safety laboratory for haematology and clinical chemistry and per the eCRF for urinalysis (i.e., a positive or negative result) with the exception of the following reference ranges for urinalysis:

- pH: 5.0 to 9.0
- Specific gravity: 1.000 to 1.030

11.5 Vital Signs

The details of measurement of vital signs (i.e., systolic and diastolic BP, heart rate, oral body temperature, respiratory rate, and clinical assessment and findings) are described in the study protocol.

11.5.1 Summary Tables for Vital Signs

Vital signs data, including change from baseline (Day 1, pre-dose for each study period), will be summarised (i.e. n, mean, SD, median, minimum, and maximum) at each post-baseline time point by regimen.

In addition, the number of subjects with ‘substantial’ increases or decreases or no substantial change from baseline in systolic BP (>20 mmHg), diastolic BP (>10 mmHg) and heart rate (>15 bpm) will be summarised.

11.5.2 Listings for Vital Signs

All individual vital signs data, including derivations, such as change from baseline, will be listed. Individual data will be flagged with an “H” or an “L” for values that are higher or lower than their reference ranges, respectively, and subjects with ‘substantial’ increases or decreases from baseline (as defined in [Section 11.5.1](#)) in systolic BP, diastolic BP, and heart rate will be flagged with an ‘I’ (increase) or ‘D’ (decrease), respectively. If applicable, data from unscheduled vital signs assessments will also be listed and flagged with a “#” to indicate it will not be used in the summary statistics.

In addition, a separate listing of all vital signs data outside their reference ranges by subject will also be provided.

The reference ranges (from Quotient SOP “The Interpretation of the Electrocardiogram, Vital Signs and Clinical Laboratory Data During Phase I”) defined in [Table 6](#) will be used.

Table 6 Vital Signs Reference Ranges

Parameter	Split	Lower limit	Upper limit
Systolic BP	18-45 years	90 mmHg	140 mmHg
Systolic BP	>45 years	90 mmHg	160 mmHg
Diastolic BP	NA	40 mmHg	90 mmHg
Heart rate	NA	45 bpm	100 bpm
Oral Body Temperature	NA	35.5°C	37.5°C
Respiration Rate	NA	10 breaths/min	24 breaths/min

NA=Not applicable

11.6 ECGs

The details of measurement of supine ECG parameters (i.e., ventricular rate, RR interval, QT interval, corrected QT interval by Fridericia's formula (QTcF), PR Interval, QRS duration, QRS axis, rhythm, interpretation, and clinical significance and findings) are described in the study protocol.

11.6.1 Summary Tables for ECGs

ECG data, including change from baseline (Day 1, pre-dose for each study period), will be summarised (i.e., n, mean, SD, median, minimum, and maximum) at each post-baseline time point by regimen.

The number and percentage of subjects with normal and prolonged QTcF and increases in QTcF intervals from baseline within the categories defined in [Table 7](#) (based on the International Council on Harmonisation [ICH] E14 guideline [\[5\]](#)) will be summarised by time point. Percentages will be based on the number of subjects with measurements at the relevant time point.

Table 7 ICH E14 Ranges for QTcF

Parameter	ICH E14 Range
QTcF	≤450 msec (normal)
	451-480 msec
	481-500 msec
	>500 msec
Increase in QTcF from baseline	≤30 msec
	31-60 msec
	>60 msec

11.6.2 Listings for ECGs

All ECG measurements (i.e., single readings), including derivations, such as change from baseline, will be listed.

All ECG measurements will be flagged with an "H" or an "L" for values that are higher or lower than their reference ranges, respectively. If applicable, data from unscheduled ECG assessments will also be listed and flagged with a "#" to indicate that it will not be used in the summary statistics.

In addition, measurements with increase in QTcF from baseline of 31-60 msec and with 'substantial increases' (>60 msec) will be flagged with 'I' and 'SI', respectively.

Separate listings of all ECG parameters outside their reference range by subject and also with QTcF increases from baseline >30 msec will also be provided.

The reference ranges (from the eCRF study build specification for all parameters, except QT Interval, which is from Quotient SOP “The Interpretation of the Electrocardiogram, Vital Signs and Clinical Laboratory Data During Phase I / II Clinical Trials”) and defined in [Table 8](#) will be used.

Table 8 ECG Reference Ranges

Parameter	Split	Lower limit	Upper limit
Ventricular Rate	NA	45 bpm	100 bpm
QT Interval	NA	NA	500 msec
QTcF Interval	Males	NA	450 msec
QTcF	Females	N/A	470 msec
PR Interval	NA	120 msec	220 msec
QRS Duration	NA	NA	120 msec
QRS Axis	NA	-30°	100°
RR Interval	N/A	600 msec	1333 msec

NA=Not applicable

11.7 Physical Examination

All physical examination details and comments on any physical examination findings will be listed.

12 Interim Statistical Analyses

No interim statistical analysis is planned for this study.

13 Changes in the Conduct of the Study or Planned Analysis

13.1 Changes in the Conduct of the Study

No changes in the conduct of the study had been reported at the time this document was written.

13.2 Changes to the Planned Analyses

No changes to planned analysis.

13.3 Any Other Relevant Changes

Not applicable.

14 Overall Considerations

14.1 Statistical Programming and Analysis

The Data Sciences Department at Quotient will perform the statistical programming and analysis to produce all analysis datasets and TFLs using the statistical SAS Software v9.4 (or more recent version).

In general terms, categorical data will be presented using counts and percentages, while continuous variables will be presented using n, mean, SD, median, minimum, and maximum. For PK data, additional statistics including CV%, geometric mean, geometric SD, and geometric CV% will be presented, as appropriate.

The geometric mean is obtained by applying a natural log transformation to the raw data, calculating the arithmetic mean of the transformed values and then back transforming the arithmetic mean.

The following formula will be used to calculate the geometric SD:

$$\text{geometric SD} = \exp\{\text{SD}[\log(\text{raw data})]\}$$

i.e., a natural log transformation is applied to the raw data, the arithmetic SD of the transformed values is calculated, and then the arithmetic SD of the transformed values is back transformed.

The following formula will be used to calculate the geometric CV%:

$$\text{geometric CV\%} = 100 \times (\exp\{\text{SD}[(\log(\text{raw data}))^2 - 1]\})^{1/2}$$

i.e., a natural log transformation is applied to the raw data, the arithmetic SD of the transformed values is calculated. This value is then squared. The square value is back transformed and a value of 1 is subtracted from the back transformed value. A square root is then applied and the resulting value is multiplied by 100.

In general summary statistics and statistical analysis results will be presented as detailed in [Table 9](#), unless otherwise stated:

Table 9 Reporting Conventions for Summary Statistics and Statistical Analysis

Data Type	Statistic	Number of decimal places for reporting (i)
Frequency	Counts (n)	None
	Percentages (%)	1 decimal place
	n	None
	Mean	i + 1 decimal places
	Median	i + 1 decimal places
	SD	i + 1 decimal places
	Min	i decimal places
	Max	i decimal places
	Q1	i decimal places
	Q3	i decimal places
Summary statistic	CV%	1 decimal place
	Geometric Mean	i + 1 decimal places
	Geometric SD	i + 1 decimal places
	Geometric CV%	1 decimal place
	Ratios (%)	2 decimal places
	Ratios *	3 decimal places
	Confidence intervals (%)	2 decimal places
	Confidence intervals *	3 decimal places
	p-values	if <0.001: presented as <0.001
		if ≥0.001 and <0.099: presented to 3 decimal places
		all other p-values will be presented to 2 decimal places
Statistical analysis	i refers to the number of decimal places reported in the eCRF or other appropriate source data for the original data. Where bioanalytical or PK data are received rounded in significant figures rather than decimal places, summary statistics will be supplied to the same precision.	
	if <0.001: presented as <0.001	
	if ≥0.001 and <0.099: presented to 3 decimal places	
	all other p-values will be presented to 2 decimal places	

i refers to the number of decimal places reported in the eCRF or other appropriate source data for the original data. Where bioanalytical or PK data are received rounded in significant figures rather than decimal places, summary statistics will be supplied to the same precision.

* Where ratios are not presented as (%) (e.g., optional assessment of dose proportionality)

Details of how the individual PK parameters will be presented are detailed in [Section 9.1.1](#). Where data requires rounding, values ending with 1 to 4 will be rounded down and values ending with 5 to 9 will be rounded up.

All data listings will be based on all enrolled subjects (as defined in [Section 3.2.1](#)). Details of age and sex will be included on all data listings.

All statistical tests relating to PK parameters will be 2-sided and will be performed using a 10% significance level, leading to 90% (2-sided) confidence intervals (CIs).

If any baseline measurements are found to be missing then consideration will be given to imputation using the preceding time point (e.g., screening, admission, if applicable). Unscheduled assessment may be used if appropriate. Details of any such imputations will be documented as part of the safety analysis set.

There will be no other imputations for the safety data with regard to missing values or study discontinuation (i.e., subjects who do not complete the study). Imputation for PK parameter estimation using WinNonlin is described in [Section 9.1.2](#) and for reporting PK data is described in [Section 9.1.3](#).

If partial dates are available for smoking history, prior medications, or medical/surgical history, there will be no date imputations. The data listings will only show the date information for the date part that is available (e.g., if only the year part of the date is available then YYYY will be presented in the listing). If the full date information is missing, then this will be presented as missing on the data listing.

If the start date/time of an AE record is missing or incomplete, preventing a clear allocation of the AE to a single treatment period, a worst-case consideration (see below) will be done aiming to allocate the AE record to one single treatment period, if possible. When a worst-case consideration is needed, any available start or end date/time will be considered in assignment of the AE to a treatment period.

- An AE which according to the available information of its start date/time could belong to screening as well as to the first treatment period will only be placed in the first treatment period
- An AE which according to the available information of its start date/time could belong to two (or more) subsequent treatment periods will be allocated to all the matching treatment periods (i.e., these AE records will be replicated and reported once in each of these matching treatment periods where IMP was administered before the end date)
- An AE which according to the available information of its start date/time could belong to all possible treatment periods will be allocated to all the treatment periods

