5.3 Study Sample Size

The study is exploratory, and no formal sample size calculation has been made. Based on experience from previous studies of a similar design, a sample size of 16 subjects and a minimum of 12 evaluable subjects is considered sufficient to meet the objectives of the study.

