9.2 Concentration and PK Summary Tables

Summary statistics (i.e., n, mean, SD, CV%, median, minimum, maximum, geometric mean, geometric SD, and geometric CV%) of concentration data will be calculated for each time point and regimen for delafloxacin in plasma. The number of BLQ values (n#) per time point will also be presented. Geometric statistics will not be calculated for Day 1, pre-dose concentrations.

Summary statistics (i.e., n, mean, SD, CV%, median, minimum, and maximum) of plasma PK parameters will be calculated for delafloxacin for each regimen. Geometric mean, geometric SD, and geometric CV% will be presented for all plasma PK parameters except Tlag and Tmax.

Non-measurable values reported in the plasma concentration data (i.e., values that are BLQ), will be entered as zero for the determination of summary statistics, with the exception of geometric means, geometric SD, and geometric CV%, where BLQ values will be imputed as half the lower limit of quantification (LLOQ) value. Data recorded as NR, NS, or NC will be handled as missing (i.e., no assumption will be made about the actual concentration).

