					Date	Start Time	End Time	Percent consumed (%)	Comments
XXX	M/35	PERIOD 3 DAY 1	XXX MG POS...	XXXX	DDMMYYYY	HH:MM	HH:MM	XX - XX	XXXX XXXX
		PERIOD 4 DAY 1	XXX MG POS...	XXXX	DDMMYYYY	HH:MM	HH:MM	XX - XX	XXXX XXXX
XXX	M/50	PERIOD 3 DAY 1	XXX MG POS...	XXXX	DDMMYYYY	HH:MM	HH:MM	XX - XX	XXXX XXXX
		PERIOD 4 DAY 1	XXX MG POS...	XXXX	DDMMYYYY	HH:MM	HH:MM	XX - XX	XXXX XXXX
...

Note: Investigational Medicinal Product is delafloxacin, POS = powder for oral suspension, Regimen B, C and D with orange flavour
Regimen Key: A = 450 mg tablet (reference) fasted, B = 450 mg POS fasted, C = xxx mg POS <status>, D = xxx mg POS <status>

PROGRAM PATH: X:\~\QSCXXXXXX\~\TFLS\PRODUCTION\LIS-XX

DDMMYYYY HH:MM

Sponsor/Quotient Sciences Confidential

Melinta Therapeutics
Protocol: ML-DEL-101-3727-1

Page x of y

LISTING 16.2.5.2
Blood Sample Collection Details for Pharmacokinetic Analysis and Plasma Pharmacokinetic Concentrations: Delafloxacin
Individual Values: All Enrolled Subjects

Subject ID	Sex/ Age	Period	Regimen	Visit	Time Point	Sample		Actual Time from Dose (h)	Parent Concentration<units>	Sample Comments
						Date	Time			
XXX	M/35	PERIOD 1	450 MG TAB FDAY 1		PRE-DOSE	DDMMYYYY	HH:MM	XX.XX	BLQ XXXX XXXX
					0.5 H	DDMMYYYY	HH:MM	XX.XX #	xx.x XXXX XXXX
					1 H	DDMMYYYY	HH:MM	XX.XX	xx.x XXXX XXXX
					1.5 H	DDMMYYYY	HH:MM	XX.XX	xx.x XXXX XXXX
				
				
...
...

Note: Investigational Medicinal Product is delafloxacin, POS = powder for oral suspension, Regimen B, C and D with orange flavour
Regimen Key: A = 450 mg tablet (reference) fasted, B = 450 mg POS fasted, C = xxx mg POS <status>, D = xxx mg POS <status>
'#' indicates sample outside of scheduled time window.

BLQ = Below Limit of Quantification. Lower Limit of Quantification (LLOQ): XX ng/mL

PROGRAM PATH: X:\~\QSCXXXXXX\~\TFLS\PRODUCTION\LIS-XX

DDMMYYYY HH:MM

Programming note: Any exclusion from summary statistics due to non-evaluable profiles or timepoint will be
shown by further footnotes and flagging

Sponsor/Quotient Sciences Confidential

Melinta Therapeutics
Protocol: ML-DEL-101-3727-1

Page x of y

LISTING 16.2.6.1
Plasma Pharmacokinetic Parameters: Delafloxacin
Individual Values: All Enrolled Subjects

Subject ID	Sex/ Age	Period	Regimen	PK Parameter 1 (units)	All PK Parameters
XXX	M/35	PERIOD 1	450 MG TAB	XXXX a d	XXXX
		PERIOD 2	450 MG POS...	XXXX	XXXX
		PERIOD 3	XXX MG POS...	XXXX	XXXX
		<PERIOD 4>	XXX MG POS...	XXXX	XXXX
XXX	M/50	PERIOD 1	450 MG TAB	XXXX	XXXX
		PERIOD 2	450 MG POS...	XXXX c	XXXX a

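### SAP 14.1: the displayed geometric CV% formula contradicts the correct description beneath it; taken literally it cannot fall below 100% and changes with the concentration unit

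*SAP*

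**What the plan says.** SAP 14.1 (Statistical Programming and Analysis) introduces the expression with "The following formula will be used to calculate the geometric CV" and displays it as "100 \times (\exp\{\text{SD}[(\log(\text{raw data}))^2 - 1]\})^{1/2".

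The explanatory paragraph immediately after it gives the steps in words. After log transformation, "the arithmetic SD of the transformed values is calculated. This value is then squared". Then: "The square value is back transformed and a value of 1 is subtracted from the back transformed value". Finally: "A square root is then applied and the resulting value is multiplied by 100".

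SAP 9.2 sets out where the statistic appears: "Geometric mean, geometric SD, and geometric CV% will be presented for all plasma PK parameters except Tlag and Tmax". The same section applies it to plasma concentrations at each time point other than Day 1 pre-dose, by regimen. The corresponding mock tables are 14.2.1 (concentrations) and 14.2.2 (parameters).

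SAP Table 2 gives concentration units only generically, as mass unit per mL. Mock Listing 16.2.5.2 shows "Lower Limit of Quantification (LLOQ): XX ng/mL".

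**The concern.** The display and the paragraph that explains it are two different calculations, and the lead-in attaches to the display. In the display, the square is applied to each log value and the 1 is subtracted from each squared log before the SD is taken. In the words, the square is applied to the SD, and the 1 is subtracted after exponentiation. Only the second is the usual geometric CV%.

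At stake is a descriptive variability figure reported for almost every plasma PK parameter and every post-dose concentration. SAP 14.2.1 requires summary tables to be checked manually with a calculator or spreadsheet. If the programmer follows one statement and the checker the other, they will disagree. If both follow the display, a wrong figure could pass QC.

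**Working it through.** The documents give no numerical geometric CV%, so there is no figure of the plan's own to reproduce. The check codes both definitions and applies them to the same data, using the n-1 SD and natural logs throughout.

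**Definitions**

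- Words: 100 x sqrt(exp(s^2) - 1), where s = SD(ln x).
- Display: 100 x sqrt(exp(d)), where d = SD((ln x)^2 - 1).

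**Properties of the display that need no data**

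- The -1 does nothing, because subtracting a constant does not change an SD.
- Since d is at least 0, exp(d) is at least 1 and the result is at least 100%. Sixteen identical values give 100% by the display and 0% by the words.
- Changing the unit by a factor k adds c = ln k to each log. Then (ln x + c)^2 = (ln x)^2 + 2c ln x + c^2, and the term 2c ln x alters d. The words are unaffected, because SD(ln x + c) = SD(ln x).

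**Worked example (five invented AUCs: 15, 18, 20, 22, 27)**

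- Logs: 2.7081, 2.8904, 2.9957, 3.0910, 3.2958, so s = 0.2197 and s^2 = 0.04825.
- Words: 100 x sqrt(exp(0.04825) - 1) = 100 x sqrt(0.04943) = 22.2%.
- Squared logs: 7.3335, 8.3542, 8.9744, 9.5545, 10.8625, so d = 1.3200 with or without the -1.
- Display: 100 x sqrt(exp(1.3200)) = 100 x sqrt(3.7436) = 193.5%.
- Same data multiplied by 1000 (ug to ng): s is unchanged and the words again give 22.2%. Now d = 4.3543, and the display gives 100 x sqrt(exp(4.3543)) = 100 x sqrt(77.81) = 882.1%.

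**Range under other assumptions**

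Sixteen subjects (the planned number in SAP 5.3) were given log-normal values at normal-score positions. The geometric mean of 7 ug/mL and the true CVs are assumptions.

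| True CV (= words) | Display, ug/mL | Display, ng/mL |
|---|---|---|
| 20% | 147.1% | 577.5% |
| 30% | 177.4% | 1345.8% |
| 50% | 253.0% | 6564.7% |

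For true CVs of 10 to 100% and geometric means of 1 to 20 ug/mL, the ratio of display to words runs from 1.5 to 13.5 in ug/mL. In ng/mL it runs from about 20 to about 3850. The size of the error is therefore not a single number; it depends on the unit and on the data.

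**A more lenient reading of the brackets**

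If the square is moved outside the SD but the -1 stays inside the exponential, the formula becomes 100 x sqrt(exp(s^2 - 1)). This no longer depends on the unit, but it gives 62.1% for the five AUCs instead of 22.2%. Its floor is 100 x exp(-0.5), about 61%. The display agrees with the words only if the -1 is moved outside the exponential as well.

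**The case against.** Four points can be made on the other side.

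1. **The brackets may be a reading artefact.** The point rests on where a superscript, a -1 and some brackets sit in one equation that a program read from a PDF. Table 9 in the same section came through visibly scrambled. This stands as a reason to check the page before changing anything. It does not dispose of the point: the brackets balance as read, and the geometric SD formula just above was read correctly and agrees with its own description.

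2. **The right method is already there.** The steps beneath the display are complete, in order and unambiguous. That is true, and it makes the correction editorial. It does not remove the contradiction, because the display is what the lead-in sentence points to.

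3. **The error would probably be caught.** An output that never falls below 100% should look odd. SAP 14.2 requires peer review of SAS code, and SAP 14.2.1 requires manual checking of tables. An independent calculation that follows the words would expose the mismatch. This is fair and lowers the practical risk, although it does not protect against both people using the display.

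4. **Little depends on it.** A reader might infer that the bioavailability or food-effect results are compromised, or that geometric CV% is the sole variability measure for the secondary PK objective. The documents support neither. The models in SAP 9.5 produce GMRs and 90% CIs from log-transformed parameters without this formula. The data required for dose and prandial selection in SAP 5.2.2 do not include it. SAP 9.2 also reports SD, CV%, minimum, maximum and geometric SD, and the secondary endpoint lists PK parameters, not geometric CV%.

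**Conclusion.** The point holds as an internal contradiction of limited reach. As read, the display in SAP 14.1 is not the geometric CV%, and the description below it is. That the literal display has a floor of 100% and depends on the unit follows from its algebra and needs no assumption about the data. The sizes (193% and 882% against 22.2%) are illustrative and rest on invented values.

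Only the descriptive geometric CV% in Tables 14.2.1 and 14.2.2 is exposed. Geometric means, geometric SDs, GMRs, 90% CIs and in-study decisions are untouched. It would go too far to say that reported figures will be wrong: that would require someone to code the display and ignore the paragraph explaining it. The conclusion also depends on the original page matching the extracted text. This is a minor correction, worth making because it is specific and cheap.

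**What to change.** Check the formula on the original page of SAP 14.1. If the brackets were altered only in the text extraction, no change is needed.

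If the page reads as extracted, replace the display with:

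geometric CV% = 100 x sqrt(exp{(SD[log(raw data)])^2} - 1)

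Keep the existing description, which already matches this, and state that the same expression applies to both programming and the manual QC in SAP 14.2.1.

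The cost is one line in the SAP. Data, models and table layouts do not change.
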